## 7. SAFETY ASSESSMENTS

Expected adverse experiences for each study intervention are as follows:

### Yoga Skills Training

- Emotional discomfort
- Muscle soreness

### Active Control

- Emotional discomfort

Expected adverse experiences to the participant related to assessment are as follows:

- Bruising or minor swelling
- Emotional discomfort

Each interventionist will monitor and note any adverse events experienced during the interventions (e.g., patients' experience of disturbed breath, expression of physical/emotional discomfort, or request to discontinue the in-person intervention sessions). In addition, interventionists will ask participants if they experienced any problems when doing the home practices and review notes from the home practice logs. These logs will be reviewed by the interventionist at each in-person session.

If a participant reports a 3 (sometimes) or higher on the item, "I thought about suicide" from the standardized PROMIS-Cancer Depressive symptoms short-form, we will inform the participant's oncologist regarding concern for depression and need for further evaluation from a mental health specialist (psychiatrist and/or clinical psychologist) within 24 hours of receiving the questionnaire (all implemented in person with the exception of the follow-up, which may be returned by mail). We will also notify oncologists if their patient verbally reports severe depressive symptoms or suicidality during the course of the study to research staff.

Two or more adverse events attributable to the interventions will prompt modification of the protocol.

## **7.1 Specification of Safety Parameters**

See previous section for safety parameters.

## **7.2 Methods and Timing for Assessing, Recording, and Analyzing Safety Parameters**

Overall, risks related to the interventions in this study are considered to be minimal and are addressed in the protocol and consent form. The study employs gentle seated movement, breathing and meditative practices or an empathic attention among people diagnosed with cancer who are receiving chemotherapy. Similar yoga interventions have been studied in patients with cancer with no published reports of adverse events, some of which included participants during the chemotherapy treatment period. The PI conducted an initial pilot study of 7 participants with the YST during chemotherapy infusions at the Mount Sinai School of Medicine from 08/2009 – 01/2010. There were no adverse events observed related to the yoga practice in this study. From 07/2011-01/13, the PI conducted a pilot study among 15 participants randomized to YST or AC during chemotherapy infusions at the CCC-WFU and observed no adverse events related to the interventions.

## **7.3 Adverse Events and Serious Adverse Events**

CTCAE term (AE description) and grade: The descriptions and grading scales found in the revised NCI Common Terminology Criteria for Adverse Events (CTCAE) version 4.0 will be utilized for AE reporting. All appropriate treatment areas should have access to a copy of the CTCAE version 4.0. A copy of the CTCAE version 4.0 can be downloaded

from the CTEP web site (<http://ctep.cancer.gov>).

**‘Expectedness’: AEs can be ‘Unexpected’ or ‘Expected’ for expedited reporting purposes only.**

- **Attribution** of the AE:

- Definite – The AE **is clearly related** to the study intervention.
- Probable – The AE **is likely related** to the study intervention.
- Possible – The AE **may be related** to the study intervention.
- Unlikely – The AE **is doubtfully related** to the study intervention.
- Unrelated – The AE **is clearly NOT related** to the study intervention.

SAEs unequivocally due to disease progression are not considered SAEs for the purposes of this study and will not be reported as such.

Only AEs related to the study intervention or measures will be captured with the exception of unexpected grade 4 Grade 5 events, which will also be documented and reported.

AEs will be labeled according to severity, which is based on their impact on the patient. An AE will be termed “mild” if it does not have a major impact on the patient, “moderate” if it causes the patient some minor inconvenience, and “severe” if it causes a substantial disruption to the patient’s well-being.

AEs will be categorized according to the likelihood that they are related to the study intervention. Specifically, they will be labeled definitely unrelated, definitely related, probably related, or possibly related to the study intervention.

Interventionists will document and report solicited AEs including physical or emotional discomfort. STM will also document self-reported ratings of 3 or higher on the suicide item from the PROMIS-Cancer Depressive symptoms measure. No additional unsolicited events will be systematically captured. Research staff will report AEs according to data safety monitoring plan. Events will be documented in the ORIS data entry system including date of event which will avoid double capture.

## **7.4 Reporting Procedures**

The PI will monitor the safety of participants on an ongoing basis by inquiring about each participant’s emotional and physical reactions during all regular study meetings with the interventionists and offer referrals by consulting with mentors when appropriate. The PI will initially assess if the AE is related to the study interventions as definitely, probably, possibly or unrelated. AEs reports will be distributed to the Independent Monitoring Committee (IMC) electronically via email.

The IMC will monitor and review adverse events and events that may be related to the intervention. This will include verification that, when indicated, these events have been reported to the appropriate agencies (e.g. IRB, NCCIH) and that such reports have been made in a timely manner. Non-serious adverse events will be reviewed on a quarterly basis by the IMC. The IMC will be notified of serious adverse events within 24 hours of occurrence and reviewed within 48 hours.

SAEs that are unanticipated, serious, and possibly related to the study intervention will be reported to the IMC, IRB, and the National Center for Complementary and Integrative Health (NCCIH) by sending the SAE Report Form via email (Appendix N: Adverse Event Form). The CCC-WFU Safety and Toxicity Reporting Committee (STRC) will also review unexpected grade 4 and all grade 5 events regardless of their attribution.

- Unexpected fatal or life-threatening AEs related to the intervention will be reported to the NCCIH Program Officer within 7 days. Other serious and unexpected AEs related to the intervention will be reported to the NCCIH Program Official within 15 days.
- Anticipated or unrelated SAEs will be handled in a less urgent manner but will be reported to the Independent Monitor(s), IRB, NCCIH, and other oversight organizations in accordance with their requirements. In the annual AE summary, the Independent Monitor(s) Report will state that they have reviewed all AE reports.

## **7.5 Follow-up for Adverse Events**

AEs will be monitored by the IMC and the PI for recurrences, resolution, and ongoing toxicities that may be related to the intervention. Documentation and reporting for follow-up AEs will occur according to reporting procedures described in Section 7.4. The duration for follow-up will be for the length of the study period while participants are enrolled in the study. If non-serious adverse events are related to the interventions, then the protocol will be modified to avoid adverse events. If the frequency of non-serious adverse events is higher than anticipated or alters the benefit risk ratio, the study investigators, after conferring with IMC, will also modify the protocol. Two or more specific adverse events among participants will prompt modification of the protocol.

## **7.6 Safety Monitoring**

The Independent Monitoring Committee (IMC) for this study is comprised of the Wake Forest School of Medicine's Institutional Data and Safety Monitoring Board members who have expertise in clinical trial methodology and conduct, biostatistics, ethics, and clinical research. The Institutional Data and Safety Monitoring Board members are not part of the key personnel involved in this grant. They are qualified to review the patient safety data generated by this study because of their unique expertise in the areas of oncology, mental health/ethics and statistics.

Study progress and safety will be reviewed quarterly (and more frequently if needed). Progress reports, including patient recruitment, retention/attrition, and AEs will be provided to the Independent Monitor(s) following each of the quarterly reviews. An Annual Report will be compiled and will include a list and summary of AEs. In addition, the Annual Report will address (1) whether AE rates are consistent with pre-study assumptions; (2) reason for dropouts from the study; (3) whether all participants met entry criteria; (4) whether continuation of the study is justified on the basis that additional data are needed to accomplish the stated aims of the study; and (5) conditions whereby the study might be terminated prematurely. The Annual Report will be sent to the Independent Monitor(s) and will be forwarded to the IRB and NCCIH. The IRB and other applicable recipients will review progress of this study on an annual basis. The PI will also send copies of signed recommendations and comments from the Independent Monitor(s) or Chair of the IMC to the NCCIH Program Officer within 1 month of each monitoring review.

## **8. INTERVENTION DISCONTINUATION**

The intervention will be discontinued for a participant if: (1) the intervention is associated with an adverse effect for a specific participant (i.e., participant does not tolerate the intervention), (2) the participant no longer is interested or willing to receive the intervention or participate in the study, or (3) the participant's healthcare provider no longer recommends that the patient receive the intervention for medical reasons or (4) the participant no longer receives chemotherapy at designated research facility. The IMC and the principal investigator will review cases upon occurrence for discontinuation of intervention.

This study will be stopped prior to its completion if: (1) the intervention is associated with adverse effects that call into question the safety of the intervention; (2) difficulty in study recruitment or retention will significantly impact the ability to evaluate the study endpoints; (3) any new information becomes available during the trial that necessitates stopping the trial; or (4) other situations occur that might warrant stopping the trial. The PI will include an assessment of futility in the annual progress report to NIH and will consult with the study monitors to assess the impact of significant data loss due to problems in recruitment, retention, or data collection.

Participants will be followed with their permission if the study is discontinued. The duration of follow-up will be length of the proposed study. We will continue to document adverse events during the follow-up period.

## **9. STATISTICAL CONSIDERATIONS**

### **9.1 General Design Issues**

Inclusion of an active control group was chosen to account for Hawthorne effects, attention from a professional, and other non-specific effects. Alternate control groups considered include a wait-list control group or stretching. Specifically, the proposed empathic attention control was chosen to control for the non-specific effects of the intervention without including any of the proposed active intervention components.

Stratified randomized control design was selected for this study to enable tighter control over known influences on outcome. Statistical control via covariate analysis would not suffice. The statistical hypotheses are:

### **Specific Aim 1 Hypothesis**

**Primary:** Yoga Skills Training (YST) will demonstrate clinically meaningful reduction in fatigue and depressive symptoms compared to an attention control group.

Fatigue and depression will be measured using the Patient-Reported Outcomes Measurement Information System (PROMIS)-Cancer specifically designed for use in cancer patients (see Section 9.5 Outcomes).

**Secondary:** Reductions in fatigue and depressive symptoms will be associated with decreases in mediators.

**Specific Aim 2 Hypothesis:** The YST will show trends for reducing levels and variability of daily fatigue and depressive symptoms to a greater degree than the AC and reductions will be associated with decreases in mediators.

**Specific Aim 3:** Qualitative data will be used to inform a larger trial.

## **9.2 Sample Size and Randomization**

The primary purpose of this study is to inform the potential efficacy of the YST in this population. Thus, it is imperative that in this initial study, effect sizes generated from the patients who successfully complete the YST protocol be used for that efficacy assessment. Furthermore will be important to understand likely differences between the patients who do successful complete the study protocol and those who do not. Therefore, patients for whom baseline and post YST/AC completion (Week 10) are available will comprise efficacy intention-to-treat (ITT) analysis sample. We used the revised CONSORT 2010 guidelines for intention-to-treat (ITT) analysis of randomized control trials in our sample considerations. Those guidelines dropped specific ITT in favor of clear descriptions of exactly who would be (or was) included in the analysis per our specification above. We also took into account considerations for minimizing missing data within the context of ITT specified by White et al. We have incorporated flexible windows for the data collection in our protocol and are allowing for possible randomly missing interim assessments. Secondary analyses will be conducted to evaluate the potential differential effect of the interventions on a one-month follow-up assessment of outcomes and changes in daily assessments of fatigue, depressive symptoms, psychological stress, and circadian disruption. Further exploratory (not hypothesis testing) analyses will be conducted with the YST study group to examine the association of dose (i.e., days of in-person sessions completed plus days of home practice), outcome expectations and efficacy beliefs with changes in fatigue, depressive symptoms, psychological stress, circadian disruption, and inflammation.

Based on prior longitudinal work with patients from similar populations, we are anticipating approximately 15% dropout (from N=44). From previous research in a mixed sample of cancer patients, the variability in the values of the PROMIS 7-item fatigue measure used in this study is a standardized standard deviation of 8 points (Mean t-score=53.6). Effect sizes in preliminary studies of yoga for fatigue as compared to an active control in patients with cancer range from 0.33 to 1.50. This variability may be explained in part by study quality and patients' initial levels of fatigue. We expect that daily assessments of fatigue and depressive symptoms will detect these symptoms at their nadir and thus may be more sensitive to such phenomena than recalled measures. Therefore, it is important to obtain a good estimate of the variance of fatigue in this group to use in future studies. Power calculations for a subsequent larger study will be based on clinically meaningful differences between the groups on the primary outcome using estimates of SD. With a sample size of 44, the probability is 0.80 (80% confidence) that the estimate of the standard deviation (SD) will be no more than 10% of the true population SD below the true population SD; if the SD varies by group, there is 80% confidence that the estimate of the SD is no more than 14% below the true SD.

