## 6.2 Description of Evaluations

Recalled assessments will be collected at four time points (baseline, mid-intervention, post-intervention, 4-week follow-up; Appendix F: Chart Review Form and Questionnaires) and a semi-structured interview conducted after completion of all assessments (either in person or by telephone; Appendix G: Semi-Structured Interview Guide). To minimize burden, all assessments via recalled questionnaires and interviews will be scheduled to coincide with the patients' appointment for chemotherapy.

Therefore, sequencing of each patient's assessments will be based on the timing of the respective patient's first completed chemotherapy visit. The standard chemotherapy timing is every two weeks. The randomized study condition will commence with the second chemotherapy visit. Given that there may be slight personal modifications to the standard schedule, we have proposed a design that will attempt to control for the possible effect of chemotherapy schedule on outcomes. If a chemotherapy visit is rescheduled for within two weeks of the standard schedule, the intervention will occur at that next visit (and all following assessments will then follow the subsequent standard chemotherapy schedule). If the rescheduled chemotherapy visit is more than two weeks later, the in-person study intervention session for that participant will not occur, the assessments will be mailed to the participant for completion, and this will be documented as an aspect of treatment fidelity.

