#### 6.2.5 Completion/Final Evaluation

The following assessments will be performed the final visit (Week 14).

- **Clinical data.** Any chemotherapy dose modifications, symptoms related to dehydration (e.g., diarrhea) and prescription medications for fatigue, sleep, anemia, depressive symptoms, and pain will be abstracted at follow-up.
- **Questionnaire:** Fatigue, Depressive Symptoms, Psychological Stress, Regulation of Psychological Stress, Circadian disruption
- **Interview (Qualitative Feedback).** A semi-structured interview will be implemented after all other data collection is complete.

Participants who discontinue study the intervention early (e.g., due to changes in chemotherapy treatment location, who choose to withdraw participation) will require no specific evaluations. The reason for discontinuation will be documented. We will contact participants to obtain follow-up data remotely if they discontinue participation due to change in treatment location. Patients terminated from the study will undergo no further monitoring once they have stopped the study intervention.

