## 9.6 Data Analyses

SAS will be used for statistical analysis. Graphical and descriptive statistical methods will be applied to examine the shapes of study data distributions and need to transform, if necessary, for inferential analyses. Per descriptions above, analyses will be conducted using intention-to-treat principles as stated in the CONSORT 2010 guidelines and flexible protocol elements to minimize missing outcome data. Missing data are expected to be of two types: 1) nonrandom (death, deteriorating condition, or other lost-to-follow-up) and 2) random (inability to make it into the clinic for one of the assessment periods). Because fatigue post-intervention is the most critical outcome assessment point, the 1st assessment (study entry) and the post-intervention assessment point at Week 10 after study entry will be required for inclusion in the hypothesis testing analysis. Randomly missing assessments at Week 10 will be handled within the statistical analysis described. Randomly missing item responses within study measures will be handled according to the instructions for each instrument when developed and validated. Missing data assessments and drop-out occurrences will be analyzed to inform future research. We do not expect those types of missing data to be random; therefore imputation procedures will not be conducted. Maximum Type I error of 0.05 (uncorrected and/or corrected as necessary) will be maintained for statistical significance and all analyses will be performed in consultation with [name].

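### The analysis set labelled ITT is a Week 10 complete-case set, and Section 9.6 contradicts itself on missing Week 10 scores

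*Combined protocol and SAP*

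**What the plan says.** Section 9.2 defines the efficacy set: "patients for whom baseline and post YST/AC completion (Week 10) are available will comprise efficacy intention-to-treat (ITT) analysis sample". It gives as the reason that it wants "effect sizes generated from the patients who successfully complete the YST protocol be used for that efficacy assessment". Section 9.3 adopts the same set by reference. Both sections allow for randomly missing interim assessments, and Section 9.2 also wants to understand how those who complete the study protocol differ from those who do not.

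Section 9.6 says that the analyses follow intention-to-treat principles and that "the post-intervention assessment point at Week 10 after study entry will be required for inclusion in the hypothesis testing analysis". Its next sentence reads "Randomly missing assessments at Week 10 will be handled within the statistical analysis described". It lists death, deterioration and other loss to follow-up as non-random causes of missing data. On missing assessments and drop-out it says "We do not expect those types of missing data to be random; therefore imputation procedures will not be conducted". The Aim 1 analysis is a mixed-effects generalised linear model.

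On data collection, Section 6.2 provides that when chemotherapy slips by more than two weeks "the assessments will be mailed to the participant for completion". Section 6.2.5 says "We will contact participants to obtain follow-up data remotely if they discontinue participation due to change in treatment location", but otherwise requires no specific evaluations after early discontinuation and adds that "Patients terminated from the study will undergo no further monitoring once they have stopped the study intervention".

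**The concern.** A set chosen by whether the outcome was observed is a complete-case set, whatever its label. Three faults follow.

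- **Label and target.** The set is not ITT, because randomised participants are removed for a post-randomisation reason. Nor is it strictly the protocol-completer set that Section 9.2 says it wants, because entry depends on a questionnaire and not on sessions attended.
- **Contradiction.** A participant without a Week 10 score cannot be both excluded from the hypothesis test and handled within it. Two analysts could build different primary datasets from this text.
- **Reasoning on missing data.** Non-random loss is given as the reason not to impute. Dropping those participants does not avoid the problem; it makes its own untested assumption. Their Week 0 and any Week 8 scores are discarded, although the planned mixed model could use them.

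At stake are the pilot's efficacy estimate, which would be reported as ITT, and possibly the SD used to size the next trial. Section 9.2 bases that later sample size on a clinically meaningful difference and the SD, so the pilot's effect estimate does not enter it.

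**Working it through.** **Inputs from the documents.** N = 44, 22 per arm (Précis); drop-out about 15% and SD 8 T-score points (9.2); primary time point Week 10 (9.5.1).

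**The plan's own figure.** Section 9.2 justifies N = 44 by the precision of the SD. The shortfall at 80% confidence is 1 − √(χ²₀.₂₀,df / df).

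- N = 44, pooled within arm, df = 42: 9.8% (plan: 10%).
- 22 per arm, df = 21: 14.2% (plan: 14%).

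Both reproduce, but they count all 44. With 44 × 0.85 = 37.4, about 37 are evaluable, and the shortfalls become 10.8% (df = 35) and, at 18.7 per arm, 15.6%.

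**Standard error of the group difference.** At 18.7 per arm, √(2/18.7) = 0.327 SD unadjusted. With an assumed correlation of 0.6 between visits, 0.327 × √(1 − 0.36) = 0.262 SD after baseline adjustment.

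**Simulation.** Assumptions, not document figures: Week 0, 8 and 10 scores normal with correlation 0.6, no true effect, 15% drop-out in each arm, logistic drop-out with log-odds 0.5, 1.0 or 1.5 per SD of fatigue. Negative values favour YST.

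| Drop-out depends on | Estimate | 0.5 | 1.0 | 1.5 |
|---|---|---|---|---|
| (a) Week 10, both arms alike | Effect bias (SD) | about 0 | about 0 | about 0 |
| | Week 10 SD ÷ true SD | 0.985 | 0.952 | 0.919 |
| (b) Week 10, YST only | Completers, unadjusted | −0.073 | −0.132 | −0.176 |
| | Completers, baseline-adjusted | −0.047 | −0.086 | −0.116 |
| | All data, Week 8 known | −0.041 | −0.074 | −0.100 |
| | All data, Week 8 also missing | −0.047 | −0.086 | −0.116 |
| | Pooled SD ÷ true SD | 0.992 | 0.977 | 0.960 |
| (c) Week 8, YST only | Completers, baseline-adjusted | −0.017 | −0.034 | −0.044 |
| | All data, Week 8 known | about 0 | about 0 | about 0 |

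- In case (b) the adjusted bias times 8 is 0.38, 0.69 and 0.93 points. Across correlations 0.8 to 0.4 it runs from 0.03 to 0.15 SD. If only AC is affected, the size is the same and the sign reverses.
- In case (a) a sample size proportional to SD² is too small by 1 − 0.985² = 3.0%, 1 − 0.952² = 9.4% and 1 − 0.919² = 15.5%.
- An all-data likelihood estimate of the SD in case (a) recovers little: 0.987, 0.961 and 0.933 with Week 8 known for everyone.

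**Unequal drop-out.** If those lost would have scored 4 to 8 points worse in both arms, the bias is the difference in drop-out rates times that shift.

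- 20% against 10%: 0.10 × 4 to 8 = 0.4 to 0.8 points.
- 30% against 0%, the extreme split at 15% overall: 0.30 × 4 to 8 = 1.2 to 2.4 points, or 0.15 to 0.30 SD. The upper end is close to the smallest effect size cited in Section 9.2 (0.33).

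**The case against.** The strongest reply is that the choice is open and reasoned. Sections 9.2 and 9.3 say who is analysed and why, limit generalisation to that sample, and Section 9.2 calls for a comparison of completers with non-completers. This is a pilot sized on SD precision, and every bias calculated above is below one standard error. All of that stands, and it limits the severity. It does not cure the ITT label, the conflict inside Section 9.6 or the absence of any all-randomised estimate. The conflict may be a slip, since Sections 9.2 and 9.3 speak of interim assessments, but the text must still be settled.

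Further points stand in part:

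- The 15% is overall drop-out with no time point, and mailing and remote contact will recover some scores. Seven excluded is therefore the plan's rate applied to Week 10, not a figure it states.
- Because most early stoppers lose Week 10, having that score will often go along with completing the protocol. The mismatch with the stated target is a secondary point.
- Section 9.2 does not say that the SD will come from Week 10 completers. The shrinkage arises only if it does.
- A mixed model repairs little of truly non-random loss, of the effect or of the SD. Better follow-up does more.
- Questionnaires cannot recover scores after death, and the analysis has to say how deaths are treated.

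**Conclusion.** The concern holds. As written, the primary comparison is a complete-case analysis carrying an ITT label, with an unresolved contradiction on missing Week 10 scores and no sensitivity analysis for the non-random loss the plan expects. About 7 of 44 participants would be excluded at the planned drop-out rate.

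Under the simulated mechanisms with equal 15% drop-out, the baseline-adjusted bias is about 0 when both arms lose alike and 0.05 to 0.12 SD when drop-out tracks Week 10 fatigue in one arm only. The Week 10 SD is 1.5 to 8% too small when both arms lose their most fatigued participants. That is less than the 10% sampling shortfall the plan accepts, but it is systematic and adds to it. These sizes rest on assumed drop-out patterns and visit correlations; the documents establish neither direction nor amount. This should be fixed, and confidence that the fault is in the text is high.

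**What to change.** 1. **Follow-up (6.2.5).** Send the Week 8, 10 and 14 questionnaires by the existing mail or remote routes to participants who stop sessions, unless they withdraw consent for data collection. This is the part that acts directly on non-random loss.
2. **Primary set (9.2, 9.3, 9.6).** Define it as all randomised participants in their assigned arm, delete the Week 10 inclusion requirement and reconcile the two sentences in 9.6. Fit the planned likelihood mixed model to all available Week 0, 8, 10 and 14 fatigue scores, with the Week 10 contrast as the estimate. State how deaths are treated. This removes case (c) where Week 8 was observed; in case (b) 0.04 to 0.10 SD remains, and there is no gain if Week 8 is missing too.
3. **Sensitivity analyses.** Keep the Week 10 completers under that name. Add a delta-shift analysis, for example 0 to 8 points (up to one SD) in either arm and in both. At 15% missing, each point in one arm moves the contrast by 0.15 point, so 8 points move it by 1.2.
4. **SD for the next trial.** Report it from the same full set with its confidence interval, and note that loss of the most fatigued participants can still make it too small.

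The cost is rewording four sections, IRB review of the amendment, one added sensitivity analysis, and at most about 21 questionnaires (3 for each of about 7 participants). There is a small burden on participants who have stopped sessions, and no extra patients are needed.

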##### **9.5.1 Primary Outcome**

**Fatigue (recalled)** "in the past seven days" will be assessed with the 7-item measure of Fatigue from the Patient-Reported Outcomes Measurement Information System (PROMIS)-Cancer specifically designed for use in cancer patients (item responses: 1 = never, 5 = always). This measure was selected for the primary outcome (at 10 weeks) because it is standardized, validated in people with cancer, and PROMIS is supported by NCCIH and the National Cancer Institute.

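### Section 9.2 expects about 15% dropout but states the precision of the SD for all 44 participants; if the SD is taken at Week 10 and the losses fall by then, the 80% bounds are about 11% and 16%, not 10% and 14%

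*Combined protocol and SAP*

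**What the plan says.** The Précis sets the target at 44 participants, 22 per group. Section 9.2 says "we are anticipating approximately 15% dropout (from N=44"), and nothing describes 44 as already inflated for that loss. The same paragraph explains that "it is important to obtain a good estimate of the variance of fatigue in this group to use in future studies", and gives the use: "Power calculations for a subsequent larger study will be based on clinically meaningful differences between the groups on the primary outcome using estimates of SD".

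The precision statement closes the paragraph. It begins "With a sample size of 44, the probability is 0.80 (80% confidence) that the estimate of the standard deviation (SD) will be no more", and the shortfall it allows is 10% of the true value. For group-specific SDs, "there is 80% confidence that the estimate of the SD is no more than 14% below the true SD".

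On who supplies the data, Section 9.2 says that "patients for whom baseline and post YST/AC completion (Week 10) are available will comprise efficacy intention-to-treat (ITT) analysis sample". Section 9.5.1 dates the outcome: "This measure was selected for the primary outcome (at 10 weeks"). Section 9.6 adds that "the post-intervention assessment point at Week 10 after study entry will be required for inclusion in the hypothesis testing analysis", and rules out imputation for dropouts.

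Neither the method behind the 10% and 14% nor the visit at which the SD is taken is stated.

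**The concern.** The paragraph states an expected loss and then does not carry it into the only calculation that supports the sample size. Section 9.2 has no power calculation for this trial, and the version 7 revision note says that the power analyses were rebased on estimating the variance. The precision of the SD is therefore the figure on which the choice of 44 rests.

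The next study is to be sized from this SD. For a fixed difference, the required sample size scales with the SD squared, so an SD that falls low leads to a study that is too small. If the relevant SD is the one at Week 10, people without Week 10 data contribute nothing to it, and the stated precision is slightly better than the plan's own dropout supports.

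**Working it through.** **Inputs.** Enrolment 44, 22 per group (Précis). Dropout about 15% (Section 9.2). Confidence 80%, on the low side only (Section 9.2). Primary outcome at Week 10 (Section 9.5.1). Reference SD 8 points (Section 9.2), which cancels out of the relative bound and serves only for scale.

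**Formula.** For normally distributed scores, the proportion by which the sample SD may fall below the true SD, with 80% confidence, is

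bound = 1 - sqrt(chi2_0.20(df) / df).

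For a common SD, df = n - 1 (one sample) or n - 2 (pooled over two groups). For one group's SD, df = n_g - 1.

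**The plan's own figures.**
- Common SD, n = 44, df 43: 1 - sqrt(35.065/43) = 9.70%. With df 42: 1 - sqrt(34.157/42) = 9.82%. Both round to 10%.
- By group, n = 22, df 21: 1 - sqrt(15.445/21) = 14.24%, which rounds to 14%.

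Both stated figures reproduce, and both use the full enrolled number.

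**After the stated dropout.** 44 x 0.85 = 37.4, so about 37 evaluable, 18-19 per group. This assumes that all of the 15% is lost by Week 10.
- Common SD, df 36: 1 - sqrt(28.735/36) = 10.66%. With df 35: 1 - sqrt(27.836/35) = 10.82%.
- By group, n = 19, df 18: 1 - sqrt(12.857/18) = 15.49%. With n = 18, df 17: 1 - sqrt(12.002/17) = 15.98%.

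**Range over the number evaluable at Week 10.**

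| Evaluable | Common SD | Each group |
|---|---|---|
| 44 (22 per group) | 9.7-9.8% | 14.2% |
| 40 (20 per group) | 10.2-10.4% | 15.0% |
| 37 (18-19 per group) | 10.7-10.8% | 15.5-16.0% |

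**Confidence at the stated margins.** The probability that the SD estimate is at least 0.90 of the true SD is 0.805-0.808 with 44 and 0.780-0.783 with 37. The probability that it is at least 0.86 of the true SD is 0.795 with 22 per group, and 0.773 or 0.764 with 19 or 18.

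**On the 8-point SD.** Common: 8 x 0.1066 to 8 x 0.1082 = 0.85-0.87 points, against 8 x 0.10 = 0.80. By group: 8 x 0.1549 to 8 x 0.1598 = 1.24-1.28 points, against 8 x 0.14 = 1.12.

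**Effect on the next study (common SD, fixed difference).** An SD exactly at the bound understates n by 1 - (1 - bound)^2. This is 19.0% at the stated 10%, and 20.2-20.5% at 10.66-10.82%.

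**Alternative method.** The normal approximation 0.8416/sqrt(2(n - 1)) gives 9.1% at 44 and 13.0% at 22, which do not match the text. At 37 it gives 9.9%, and at 19 or 18 per group 14.0% or 14.4%, which do.

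**The case against.** The strongest reply is that no stated number is wrong. The sentence names 44, the figures are right for 44, and the dropout rate stands openly in the same paragraph. That is true, and it makes this an omission rather than a miscalculation.

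Second, Section 9.2 does not say that the SD comes from Week 10 completers. The rule requiring Week 10 data governs the efficacy and hypothesis-testing samples, and fatigue is also measured at other visits. Section 4.3 places randomization after the baseline assessments, so a baseline SD could use all 44 and the figures would stand. This remains open. The Week 10 reading is an inference from the stated use of the SD and the dating of the primary outcome.

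Third, 37 evaluable is an assumption. The dropout is not dated, and participation runs to about 14 weeks. Section 6.2 mails assessments when a chemotherapy visit slips by more than two weeks, and Section 6.2.5 contacts people who change treatment location. Section 9.6 also says that randomly missing Week 10 assessments are handled within the analysis, which sits awkwardly with its own Week 10 inclusion rule but counts against treating every missing value as lost. At 40 evaluable the common-SD bound still rounds to 10%, although the by-group bound is 15.0%.

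Fourth, a normal approximation applied after dropout would give about 10% and 14%. The method is not stated, so this cannot be excluded. It does not rescue the wording, because 44 would then be the wrong number to name.

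A reader might go further and infer that the trial is too small, or that enrolment must rise to 52 (44/0.85) to keep 44 evaluable. The documents do not support that: no precision threshold is set as a requirement, and the change is small. Nor should the shortfall in one group's variance be read as the shortfall in the next study's sample size, since a two-group comparison depends on both variances.

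**Conclusion.** The point holds as a minor gap in how the sample size is justified. On two assumptions, that the SD is the Week 10 SD and that the whole 15% is lost by Week 10, the 80% bounds are about 11% for a common SD and 16% for each group, against the stated 10% and 14%. That is about 1 to 2 percentage points, or confidence of about 78% and 76-77% at the stated margins. With fewer losses the gap narrows, and for a baseline SD it disappears. The calculation also assumes normally distributed scores. No conclusion about the design or feasibility of the trial depends on this.

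**What to change.** Restate the sentence in Section 9.2 for the evaluable Week 10 sample and name the method. For example: with about 37 evaluable at Week 10 (44 enrolled, 15% dropout), there is 80% confidence that the SD estimate is no more than about 11% (common SD) or 16% (each group) below the true SD, by the chi-square method. If a baseline SD or a post-dropout approximation was meant, state that time point, the matching number and the method instead.

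The cost is one sentence and a stated precision about 1 to 2 percentage points less favourable. Enrolment, design and analysis do not change.
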